Primary Aims:	
To examine the effects of cigarettes that vary in nicotine content on the number of cigarettes smoked, smoke-free days, extent of uptake of non-combusted alternative nicotine-containing products, and extent of exposure to tobacco toxicants in the context of a marketplace with alternative nicotine-containing products.
 
We hypothesize that subjects in VLNC vs. NNC cigarette condition will experience: 1) fewer cigarettes smoked; 2) greater number of smoke-free days; 3) greater uptake of alternative nicotine/tobacco products; and 4) less toxicant exposure.
 
Exploratory analysis will examine whether the type (e.g., electronic nicotine delivery systems) and extent of use of alternative products mediates further reductions in cigarettes and toxicant exposure.

Secondary Aim :	
Secondary Aim 1: To examine the characteristics of products alternative to cigarettes that are chosen and to better understand responses to these various products among smokers assigned to VLNC vs. NNC cigarettes.
 
We hypothesize that across conditions, flavored electronic nicotine delivery systems with higher doses of nicotine will be preferred over other non-combustible products. Moreover, among subjects who try them, non-combusted products will be rated more positively and as providing greater withdrawal relief in the VLNC as compared to NNC conditions.
 
Secondary Aim 2: To explore variables that predict responses to the marketplace.
 
We hypothesize that a variety of factors (i.e., dependence severity, age, sex, racial ethnic group, SES) will impact product use patterns (e.g., the amount of non-combusted vs. combusted products used and days smoke-free within NNC and VLNC cigarette conditions).

Population:	Cigarette smokers

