1.2. Secondary Objectives

1.2.a Secondary Aim 1: To examine the characteristics of products alternative to cigarettes that are chosen and to better understand responses to these various products among smokers assigned to VLNC vs. NNC cigarettes.

- We hypothesize that across conditions, flavored electronic nicotine delivery systems with higher doses of nicotine will be preferred over other non-combustible products. Moreover, among subjects who try them, non-combusted products will be rated more positively and as providing greater withdrawal relief in the VLNC as compared to NNC conditions.

1.2.b Secondary Aim 2: To explore variables that predict responses to the marketplace.

- We hypothesize that a variety of factors will impact product use patterns (e.g., the amount of non-combusted vs. combusted products used and days smoke-free within NNC and VLNC cigarette conditions).

2. Background

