Rationale for a Real World Marketplace. The potential effects of RNC cigarettes on use of other tobacco products are illustrated by the findings from several studies. First, even in studies that required smokers to only smoke RNC cigarettes, a significant number smoked usual brand cigarettes, indicating the smokers needed to supplement the reduced nicotine in the study cigarettes with their own cigarettes. For example, in a gradual nicotine reduction study conducted by Benowitz et al.,¹² 10% (N=59) of smokers (not seeking treatment) assigned to RNC cigarettes withdrew during the tapering phase and 21% (N=53) of subjects who completed the tapering phase reported smoking some commercial cigarettes. In Hatsukami et al.,¹³ about 30.4% (N=37) of smokers (seeking smoking cessation treatment) who were assigned to 0.6 mg/g nicotine content cigarettes (0.05 mg machine determined nicotine yield) for six weeks used non-assigned tobacco products in the first week and by six weeks, about 5.3% (N=32) reported using such products. These rates are likely to be underestimates because they were not biochemically verified. For example, in the large study conducted by Donny et al.,¹⁴ in a secondary analysis of product non-compliance, about three-fourths of participants using the 0.4 mg/g nicotine content cigarettes (0.04 mg machine determined nicotine yield) were biochemically confirmed to be using some non-study tobacco products based on levels of total nicotine equivalents (TNEs).

In a study conducted by Hatsukami et al.,¹⁶ smokers assigned to VLNC with access to alternative nicotine delivery systems (ANDS) reported greater uptake of these products compared to those assigned to normal nicotine content cigarette; and they also experienced significantly greater reductions in combusted product use, nicotine exposure, cigarette dependence and higher number of quit attempts. Furthermore, the amount of non-combusted ANDS use was significantly, negatively associated with the amount of combusted product use and levels of carcinogen exposure, and positively related to number of abstinence days.

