Predictors of use of alternative nicotine/tobacco products: In the aforementioned study on the impact of nicotine content on the use of ANDS,¹⁶ predictors of greater use of these alternative products were being male and non-white, reporting higher dependence, and having higher education and income levels (all p's < 0.0001). Some of these results are concordant with results from Donny et al.,¹⁴ in which indicators of dependence (cigarettes per day, urinary total nicotine equivalents) were associated with non-compliance with study cigarette use only, which could be a proxy for when smokers feel the need to seek alternative sources of nicotine. The predictor variables are also consistent with the literature that shows that men are more sensitive to nicotine than women,^{22,23} that dependence severity predicts the need for higher nicotine doses,²⁴ and that use of alternative products, particularly electronic nicotine delivery systems, is greater among those with higher education.^{25,26} These results underscore the need to further investigate how different populations of smokers will respond to a national nicotine reduction policy.

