5.2.2. Phase 1: Baseline Procedures for Baseline Visits 1 (93) and 2 (92)

During Phase 1 of baseline (screening up to access to tobacco marketplace), eligible subjects will continue to smoke their preferred brand as usual. At the baseline clinic visits, subjects will complete several measures and provide biomarker samples as described below.

A. *Physiological Measures at Baseline (93 and 92):*

- 1) BrAC, which must be below 0.03 g/210L. If over the 0.03, the visit will be delayed until the level drops within range or subject can be rescheduled. If above 0.05, the visit will be rescheduled. Multiple baseline elevated BrAC results may result in discontinuation of the subject at the PI discretion. (BrAC was discontinued in conversion to telehealth visits.)
- 2) Expired breath CO level.
- 3) Vitals signs (blood pressure, heart rate).
- 4) Weight.
- 5) First morning void urine collected.
- 6) Saliva samples:
 - a) Saliva sample obtained with Salivette (with citric acid preparation) to be used for nicotine metabolite ratio (NMR) Visit 1 (93) only.
- 7) Spot urine for pregnancy tests [hCG detection] will be performed for female participants of childbearing potential (not surgically sterilized or 2 years post-menopausal) at Week

92 prior to offering Marketplace. (Pregnancy tests are performed on first morning void after conversion to telehealth visits.)

B. Questionnaires and Assessments at Baseline (93 and 92):

B.1 Web-based data collection program completed by the subject:

- 1) Minnesota Nicotine Withdrawal Scale (MNWS).
- 2) Questionnaire of Smoking Urges- Brief - Usual Brand Cigarette (QSU).
- 3) Cigarette Evaluation Scale – Baseline (CES – Usual Brand).
- 4) Respiratory and Global Health Questionnaire.
- 5) If monitored for psychiatric illness: Beck Depression Inventory 2nd Edition (BD-II) (paper only).
- 6) Cigarette Dependence Measures (Usual Brand - Visit 93 only).
- 7) Environmental Tobacco Smoke Exposure Questionnaire (Visit 93 only).
- 8) Social and Environmental Influences on Tobacco Use (Visit 93 only).
- 9) Dietary Intake (e.g., charred and smoked meats and fish) (Visit 93 only).
- 10) NIAAA Alcohol Use Questionnaire - 1 month version (Visit 93 only).
- 11) Expected Utility (ANDS) (Visit 93 only).
- 12) Perceived Health Risk of no tobacco use, usual brand cigarettes, very low nicotine cigarettes, smokeless tobacco/snus/nicotine pouches, medicinal nicotine, ENDS (Visit 92 only).
- 13) Product Expectancy Questionnaire (Visit 92 only).

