5.3. Exploratory Endpoint

- Non-combusted tobacco/nicotine products use: the number of days using any non-combusted tobacco/nicotine products in Phase 3.
- Characteristics' of products chosen (type, flavor, nicotine strength).
- Biomarkers: percent change in biomarkers (Total Nicotine Equivalents, total NNAL, mercapturic acids at the weeks 4, 8 and 12 visits during Phase 3 as compared to the last visit in Phase 2).
- Product satisfaction (Product Evaluation Scale if they used the product since the last visit; Cigarette Evaluation Scale if they smoked cigarettes since the last visit).
- Perceived health risk (Phase 1, Phase 2 and end of week 12 of Phase 3: all products for all subjects).
- Measures of discomfort/dysfunction: MNWS-R, QSU, CESD (NNC vs VLNC cigarettes irrespective of use of products).
- Dependence (FTND, WISDM, PATH items; monthly for study cigarettes).

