6.1. General Approach

All statistical analyses will be performed using SAS or R. All statistical tests will be two-tailed. A Bonferroni multiple-comparisons adjustment will be used to account for multiple comparisons for each of the two primary endpoints ($\alpha = 0.025$). Analyses of the secondary and exploratory endpoints will not be adjusted for multiple comparisons ($\alpha = 0.05$). All analyses will be completed using the intent-to-treat principle unless otherwise noted. Methods for handling missing data will be specified below.

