6.5. Exploratory Endpoint Analysis

- For the number of days of non-combusted tobacco/nicotine products use, we will use Poisson or negative binomial regression, adjusting for baseline value, study site, whether the visit is pre-COVID or not, and any baseline characteristics which are different at $p < 0.20$.
- We will descriptively examine the characteristics of the various products that are chosen (type, nicotine strength, flavor).
- For other biomarkers, similar analyses to Secondary Endpoint will be performed.
- Product satisfaction (Product Evaluation Scale, Cigarette Evaluation Scale) at the first time a participant tried a product will be summarized using mean and standard deviation and compared between two treatment arms using linear regression.
- Repeated measures of perceived health risk will be analyzed using the mixed effects model as described in Section 6.3.2.
- Discomfort as assessed by MNWS-R, QSU, CESD will be compared between the VLNC vs. NNC cigarette conditions. The methods for comparing discomfort measures between VLNC and NNC cigarettes will be the same as for those described for the primary endpoints in Section 6.3.
- Repeated measures of dependence of study cigarettes will be analyzed using mixed effects model described in Section 6.3.2.
- We will examine the cross-sectional associations of non-combusted products use with cigarettes smoked and biomarkers at different visits using marginal generalized estimating equations (GEE) model (Diggle et al, 2002, Chapter 12) with the non-combusted product use as the independent variable.
- We will explore baseline predictors of responses. We will use multivariable regressions to determine predictors of product use patterns, e.g., non-combusted product use, combusted product use, and smoke-free days. Predictor variables (depending on the responses measured) will include baseline CPD, total nicotine equivalents, FTND, age, sex, racial ethnic group, SES, perceived risk of products, product expectancy, product utility, social and environmental influences, contemplation ladder, menthol cigarette use, and nicotine metabolite ratio (NMR, reflecting rate of nicotine metabolism). Similar regression models as described in Sections 6.3 and 6.4 will be used.

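### First-try product ratings are compared by arm only among people who chose the product, with no covariates named, so a different mix of triers can appear as a difference in liking

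*Combined protocol and SAP*

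**What the plan says.** Product satisfaction is an exploratory endpoint. SAP 5.3 restricts it to users: "Product Evaluation Scale if they used the product since the last visit", with a matching condition for the Cigarette Evaluation Scale (CES). SAP 6.5, repeated in protocol 16.6.5, says that ratings at a participant's first try "will be summarized using mean and standard deviation and compared between two treatment arms using linear regression". No covariate is named. In the same section, the bullet on days of non-combusted use lists its covariates, and the bullets on perceived risk, discomfort and dependence refer back to the models of SAP 6.3. The rating bullet does neither.

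The hypothesis served is in Secondary Aim 1 (protocol 1.2): "among subjects who try them, non-combusted products will be rated more positively" under VLNC than under NNC. The primary aim in the Study Synopsis also hypothesises "greater uptake of alternative nicotine/tobacco products" under VLNC. The protocol's background reports that in an earlier study "smokers assigned to VLNC with access to alternative nicotine delivery systems (ANDS) reported greater uptake of these products" than those given normal-nicotine cigarettes, and that "predictors of greater use of these alternative products were being male and non-white, reporting higher dependence, and having higher education and income levels".

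Exploratory endpoints are tested at a two-sided 0.05 without multiplicity adjustment (SAP 6.1). The sensitivity analyses for missing data in SAP 6.8 cover primary and secondary endpoints only.

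**The concern.** Randomisation makes the arms comparable as randomised. It does not make the triers in one arm comparable with the triers in the other when the arm itself changes who tries. The plan expects exactly that, and its own background says that people who take up alternatives differ from those who do not. If VLNC smokers try products that they would have passed over under NNC, or try them for other reasons such as withdrawal relief, the arm coefficient mixes two things: how the assigned cigarette changes liking, and who is in the comparison.

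No other planned analysis compares product ratings by arm, so this is the test of the rating hypothesis in Secondary Aim 1. The background says that no earlier study has compared subjective responses to these products when cigarettes of different nicotine content are available, so the result may be read as first evidence.

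**Working it through.** The documents give no try rates, rating SD, power or target difference for this endpoint, so there is no stated figure to reproduce. The check has two parts.

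**1. Is trying affected by arm, and are predictors of it available?**

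- Arm is expected to affect trying: primary hypothesis and earlier study, as quoted above.
- Randomisation takes place at the end of Visit 00 (protocol 5.2.4).
- Collected before that: expected utility (Visit 93), product expectancy (Visit 92), perceived health risk (Visits 92 and 00), cigarette dependence including FTND (Visits 93 and 00). Baseline CPD, sex, age, race and education are in the baseline list of SAP 6.2. Income is in the demographics form (protocol 5.7.3).
- The last bullet of SAP 6.5 already names expectancy, utility, perceived risk and FTND among the predictors to be explored for product use. The rating model uses none of them.

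**2. How large could the distortion be?**

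Assumptions, none from the documents: each person's rating is standard normal and unaffected by arm. A person tries the product when a latent propensity, correlated ρ with the rating, exceeds a cut-off set by arm. With try rate p, c = Φ⁻¹(1 − p) and m(p) = φ(c)/p:

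- mean rating among triers = ρ · m(p)
- spurious difference (VLNC − NNC) = ρ · [m(p_VLNC) − m(p_NNC)]
- variance among triers = 1 − ρ² · m(m − c)

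m(30%) = 1.159, m(40%) = 0.966, m(60%) = 0.644.

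- 30% versus 40%: 0.966 − 1.159 = −0.193. Times 0.2 gives −0.04 SD; times 0.5 gives −0.10 SD.
- 40% versus 60%: 0.644 − 0.966 = −0.322. Times 0.2 gives −0.06 SD; times 0.5 gives −0.16 SD.

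Example of the rejection rate at 40% versus 60%, ρ = 0.3 and 160 per arm (400 × 0.8 / 2): triers number 64 and 96, variances are 0.938 and 0.948, SE = √(0.938/64 + 0.948/96) = 0.157, and bias/SE = −0.097/0.157 = −0.62. A two-sided 0.05 test then rejects 9.5% of the time.

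| Trying, NNC vs VLNC | ρ | Spurious difference (SD) | Rejection rate at nominal 5% (160 to 200 per arm) |
|---|---|---|---|
| 30% vs 40% | 0.2 | −0.039 | 5.5 to 5.6% |
| 30% vs 40% | 0.5 | −0.097 | 8.6 to 9.6% |
| 40% vs 60% | 0.2 | −0.064 | 6.9 to 7.4% |
| 40% vs 60% | 0.3 | −0.097 | 9.5 to 10.6% |
| 40% vs 60% | 0.5 | −0.161 | 19.3 to 23.0% |
| 50% vs 50% | any up to 0.5 | 0 | 5% |
| 95% vs 98% | 0.5 | −0.030 | 5.8 to 6.0% |

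The difference is also zero at any try rates if ρ = 0. The last row stands for study cigarettes, if nearly everyone smokes them.

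**What adjustment does.** In a simulation of 2,000,000 subjects at 40% versus 60% and ρ = 0.3, adding a baseline covariate to the regression left 0.00 SD when it carried all of the liking–trying correlation, −0.05 SD when it carried half, and −0.10 SD when it carried none.

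**The case against.** The restriction is declared. The endpoint is exploratory, its definition limits it to users, and the hypothesis is worded for people who try the product. Nothing in SAP 6.5 calls the result a causal effect of the assigned cigarette. All of this stands, and a descriptive comparison among triers is legitimate.

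A reader might infer a breach of intention to treat. The documents do not support that: SAP 6.1 says "All analyses will be completed using the intent-to-treat principle unless otherwise noted", and the endpoint definition notes the restriction.

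A reader might also infer that the plan specifies an unadjusted model. It does not say so; the absence of covariates is read from silence. But the neighbouring bullets name covariates or point to a model, so an analyst following the text would have no covariate list for this one.

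Nor do the documents support a claim that the test is biased against VLNC, or by a known amount. The negative signs in the table come from the model, in which VLNC only lowers the threshold for trying. If VLNC instead draws in people with more reason to like the product, the sign can reverse.

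Finally, the alternatives are on offer in Phase 2 and rated at Visits 91 and 00, before randomisation. If first tries there count, they cannot have been selected by arm, and the distortion is diluted. SAP 6.5 does not say whether they count.

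**Conclusion.** The point holds as a limited one. Among triers the arm coefficient is not protected by randomisation, the plan itself expects trying to differ by arm, and the regression names none of the predictors already collected. With no true effect, the spurious difference is 0.04 to 0.10 SD at 30% versus 40% trying and 0.06 to 0.16 SD at 40% versus 60%. These figures rest on assumed try rates, a liking–trying correlation of 0.2 to 0.5, and one selection mechanism shared by both arms. The direction is unknown.

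The point mainly concerns the Product Evaluation Scale for alternative products. The fault would lie in reading the difference as an effect of the assigned cigarette, not in making the comparison.

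**What to change.** In SAP 6.5 and protocol 16.6.5:

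1. Adjust the rating model for predictors of trying and liking collected before randomisation: product expectancy, expected utility, perceived risk, FTND, baseline CPD, sex, age, race, education, income and site.
2. Report try rates by arm, for each product rated.
3. Describe the result as a comparison among triers, not as an effect of the assigned cigarette.
4. Optionally, add inverse-probability-of-trying weights from the same variables as a sensitivity analysis. This shares the assumption that measured covariates explain who tries.
5. State whether first try means first in the study or first in Phase 3. Include Phase 2 use of the product as a covariate only under the second meaning. Under the first, it is zero for every first try made in Phase 3, and otherwise mainly marks when the rating was given.

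A composite defined in everyone randomised, such as having tried the product and rated it above the scale midpoint, should not serve as a test of liking. If arm has no effect on liking, liking is unrelated to trying, and half of triers rate above the midpoint, 40% versus 60% trying gives 0.40 × 0.5 = 20% versus 0.60 × 0.5 = 30%: a 10-point gap from uptake alone.

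The cost is a little more analysis code and text, with no new data. Bias is removed only as far as the measured covariates explain who tries.

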6.6. Subgroup Analyses

Subgroup analyses will play an important role in understanding the effect of nicotine reduction for different subpopulations. We will explore the effect of VLNC vs. NNC within subgroups defined by age (18-44 and 45+) or sex. We will also conduct subgroup analysis by the time of the participant being recruited, pre- or post-COVID. Subgroup analysis will follow the same approach described above as for the overall sample, but significance will be assessed by a Bonferroni-adjusted type-I rate ($\alpha/2$ for a sex group or an age group, where α is the type-I error pre-specified for a specific outcome variable for the overall sample; See Section 6.1 for the values of α).

Formal testing of the interaction between subgroup and treatment effect is not the primary concern of our subgroup analyses. Instead, subgroup analyses will provide information about the consistency of the treatment effect across subgroups, which will provide supplementary information for full understanding of the relationship between the studied interventions and the study endpoints.

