3.2.3 Power re-estimation

The power re-estimation is based on a total of 500, 450, and 400 enrolled subjects with a 20% attrition rate over the 12-week post randomization period. Power analysis was performed for the two primary outcomes: CPD smoked at the end of Phase 3 and smoke-free days during Phase 3. The effect of the two primary outcomes was assumed to be the same as previously assumed: 7 and 15 mean CPD for the VLNC and NNC group; and a 11 day difference (we assumed 12 abstinence days vs. 1 abstinence day, out of 84 days, previously) in the smoke-free days for VLNC vs. NNC. The nuisance parameters were based on the interim analysis (see Section 6.9 and Table 1 above).

The two-sided type-I error rate for each outcome (CPD and abstinence) was set at $\alpha=0.025$ ($=0.05/2$ outcomes by the Bonferroni method) for the overall sample as previously designed. The type I error rate for the gender subgroup analysis was set to be α divided by the number of subgroups ($=2$) as previously designed. The type I error rate for the age subgroup analysis was set to be α divided by 2, rather than 3 because based on the interim data, there were <1% of participants in the 18-24 age group, hence, this age group was dropped from the power analysis. The Subgroup Analysis section (Section 6.6) in the SAP was revised accordingly.

The same statistical methods were used as previously designed. Specifically, t-test was used for the CPD outcome. For the smoke-free days outcome, we first calculated the rate of smoke-free days by dividing the number of smoke-free days by the total number of days in Phase 3 (84 days) and then used z-test for the Poisson rate difference. PASS 14 was used for power calculations.

The estimated power for 500, 450, and 400 subjects is presented in Table 2.

Table 2. Power Analysis for Total Enrolled N=500, 450, and 400

Primary outcomes	VLNC	NNC	Overall sample	³ Subgroup analysis by sex		⁴ Subgroup analysis by age		
				F	M	18-24	25-44	45+

N enrolled = 500								
¹ Cigarettes (study or non-study) per day smoked at the end of Phase 3 (calculated as mean CPD based on 7 days' IVR data before the week 12 visit)	7	15	>.99	>.99	>.99	-	>.99	>.99
² Number of smoke-free days during Phase 3 (12 weeks or 84 days)	11 days difference		.94	.55	.61	-	.72	.41
N enrolled = 450								

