4.2. Definition of Sub-Group Population in Different Analyses

We intend to complete pre-planned subgroup analyses by sex, age groups (18-44, and 45+), and whether the participant was recruited pre- or post-COVID. Subgroup analysis will allow us to evaluate the consistency of the effect of VLNC vs. NNC across important subgroups.

5. Trial Endpoints

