6.9. Interim Analyses

6.9.1. Interim Analysis for Sample Size Re-estimation (see above)

One interim analysis was conducted for sample size re-estimation. Nuisance parameters were estimated based on non-comparative data, whereas the significance level, the desired power, and the assumed targeted difference in outcome due to treatment assignment were not changed. In general, sample size re-estimations based on non-comparative data are expected to have a negligible effect on the Type I error (USDHHS, FDA, CDER, and CBER, 2018).

First, we calculated the distribution of gender and age (18-24, 25-44, and ≥ 45 years old). For the outcome of CPD, we calculated the variance for the pooled sample. For the outcome of cigarette abstinence, we evaluated the control (NNC) group’s average rate of abstinence, which is calculated as the total number of smoke-free days observed among randomized participants divided by the total number of IVR days during Phase 3 (12 weeks).

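### The plan aims to judge consistency of the VLNC effect across subgroups but names no between-subgroup contrast, interval or comparison scale; separate within-subgroup significance verdicts cannot supply one.

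*Combined protocol and SAP*

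**What the plan says.** SAP 4.2 gives the purpose: "Subgroup analysis will allow us to evaluate the consistency of the effect of VLNC vs. NNC across important subgroups". SAP 6.6 repeats it, saying that "subgroup analyses will provide information about the consistency of the treatment effect across subgroups", and calls this supplementary information. The factors are sex, age (18-44 and 45+) and recruitment before or after COVID.

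On method, SAP 6.6 says "Subgroup analysis will follow the same approach described above as for the overall sample". Each subgroup therefore gets its own estimate from the models in SAP 6.3.1: linear regression for cigarettes per day (CPD), and Poisson or negative binomial regression for smoke-free days. On judgement, "significance will be assessed by a Bonferroni-adjusted type-I rate", which is alpha/2 for a sex or age group; no level is given for the COVID split. On comparing subgroups, the only statement is that "Formal testing of the interaction between subgroup and treatment effect is not the primary concern of our subgroup analyses".

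Protocol 16.4.2 and 16.6.6 carry the same text.

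**The concern.** Consistency is a statement about the difference between two subgroup effects. The plan provides two separate effects and two separate verdicts, but no planned figure for how far the effects differ or how precisely that difference is known. Verdicts can split when the effects are equal, because each subgroup has limited power. They can also agree when the effects differ, because both may be large enough to be detected.

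The comparison scale is open too. The power section works with a difference in smoke-free days, whereas the planned regression usually reports a rate ratio. Two subgroups can be equal on one scale and unequal on the other. If the scale is chosen after the results are seen, it can settle the conclusion. A reader of the smoke-free-day results by sex or age would be left to improvise.

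**Working it through.** **Inputs.** From SAP Table 1, share of sample and NNC smoke-free rate: female 44.7%, 4.52%; male 55.3%, 5.48%; age 25-44 53.4%, 2.85%; age 45+ 44.7%, 8.04%. From SAP 3.2.3: effect 11 of 84 days (0.1310), 20% attrition, overall alpha 0.025, hence 0.0125 within a subgroup (z = 2.498). At N=400 this leaves 160 analysed per arm. Ages 25-44 stand in for 18-44.

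**1. Reproduce the stated powers.** The SAP says "we first calculated the rate of smoke-free days by dividing the number of smoke-free days by the total number of days in Phase 3", and then applies a z-test for a Poisson rate difference. Treating each person as one exposure unit:

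power = Φ(d / √[(r0 + r1)/n] − 2.498), with d = 0.1310, r1 = r0 + d, n = 160 × share.

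For women, n = 71.5 and SE = √[(0.0452 + 0.1762)/71.5] = 0.0556, so power = Φ(2.354 − 2.498) = 0.443.

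| N=400 | Female | Male | 25-44 | 45+ |
|---|---|---|---|---|
| Stated | .43 | .50 | .61 | .32 |
| Recomputed | .443 | .505 | .616 | .327 |

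**2. Chance that exactly one subgroup is significant when both true effects are 11 days.** Subgroups are independent, so the chance is p1(1 − p2) + p2(1 − p1). With the stated powers:

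- N=400, sex: .43 × .50 + .50 × .57 = .50
- N=400, age: .61 × .68 + .32 × .39 = .54
- N=450, sex: .49 × .44 + .56 × .51 = .50
- N=450, age: .67 × .63 + .37 × .33 = .54

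**3. Is that variance credible?** One Poisson unit per person gives a person's smoke-free proportion a variance of r. A proportion cannot exceed r(1 − r). For VLNC women r = 0.0452 + 0.1310 = 0.176, so the plan uses 0.176 against a maximum of 0.145. With 84 daily reports the variance is r(1 − r)[1 + 83ρ]/84, where ρ is the within-person correlation between days. The documents do not give ρ; the interim control rate is only a per-day proportion, "calculated as the total number of smoke-free days observed among randomized participants divided by the total number of IVR days during Phase 3". I therefore vary it as an assumption (N=400, difference scale, same ρ in all groups, no baseline adjustment):

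| Assumed ρ | Split, sex | Split, age | Interaction SE in days, sex / age | 95% half-width in days |
|---|---|---|---|---|
| 0.2 | .001 | .007 | 2.70 / 2.79 | 5.3 / 5.5 |
| 0.4 | .099 | .158 | 3.76 / 3.89 | 7.4 / 7.6 |
| 0.6 | .304 | .369 | 4.59 / 4.74 | 9.0 / 9.3 |
| 0.8 | .442 | .494 | 5.28 / 5.46 | 10.3 / 10.7 |
| Plan's variance | .50 | .54 | 6.40 / 6.66 | 12.6 / 13.0 |

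The interaction SE is 84 × √(SE1² + SE2²).

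**4. Agreement when effects differ.** As an illustration of mine, let one subgroup gain 22 days and the other 11. On the difference scale at N=400, both are significant in 99-100% of trials at ρ = 0.2 and 85-99% at 0.4, so the verdicts match although one effect is double the other. The 95% interval for the interaction in days excludes zero in 96-97% of trials at 0.2, 75-78% at 0.4, 58-61% at 0.6, 47-49% at 0.8, and 31-34% on the plan's variance.

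**5. Scale.** An equal 11 days gives rate ratios of (0.0285 + 0.1310)/0.0285 = 5.6 at age 25-44 and (0.0804 + 0.1310)/0.0804 = 2.6 at 45+. For sex the ratios are 3.9 and 3.4.

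**6. CPD.** With a difference of 8 and the Table 1 SDs, every subgroup power exceeds .99 and the split rate is under 1%.

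**The case against.** The best defence is that the plan never adopts the rule these figures test. It calls the subgroup work exploratory and supplementary, does not forbid an interaction estimate, and nowhere says that matching or split verdicts decide consistency. A reader might infer that it does, since significance at alpha/2 is the only criterion stated, but the text does not support that. This stands: the fault is a gap in specification, not a wrong decision rule.

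A reader might also infer that the plan has no effect scale at all. It has one within each subgroup, implied by the planned models: a mean difference for CPD and, with the usual log link, a rate ratio for smoke-free days. Only the scale for comparing subgroups is missing. Because the sex groups, like the age groups, are disjoint, anyone given both estimates and standard errors could form the contrast. The plan does not commit to reporting it, or to intervals.

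Third, the 50% and 54% should not be read as the error rate to expect. They inherit a variance above the possible maximum, and at low correlation the splits almost vanish. They also concern an effect equal in days; on a ratio scale the same scenario is not homogeneous. All of this stands. Low correlation does not rescue the verdicts, though, because they then agree even when one effect is twice the other.

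Finally, an interaction estimate may be imprecise. That is true, but a wide interval shows that consistency is uncertain, which two verdicts do not.

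**Conclusion.** The point holds as a specification gap of modest priority. The documents set consistency across subgroups as an aim and provide no estimate of it: no between-subgroup contrast, no interval and no scale for the comparison. Within-subgroup verdicts cannot fill that place. For smoke-free days with an equal 11-day effect, how often they split depends on a correlation the documents do not state. The range is about 0-1% at 0.2, 10-16% at 0.4, 30-37% at 0.6 and 44-49% at 0.8 (N=400), and about half if the Table 2 powers are taken at face value. These figures assume 20% attrition, one correlation throughout, the difference scale and no baseline adjustment, which could lower the variance by an unknown amount. For CPD the problem is negligible under the stated assumptions. No figure can be given for the COVID split, for which the plan states neither alpha nor power. Nothing here touches the primary analyses.

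**What to change.** In SAP 6.6 and protocol 16.6.6, for each primary endpoint and each factor (sex, age 18-44/45+, pre/post-COVID), add the subgroup main effect and the treatment-by-subgroup interaction to the full-sample primary model. Report the interaction estimate with its 95% confidence interval as supplementary evidence, not as a p-value gate. Name one scale in advance: the mean difference for CPD; for smoke-free days, either model-standardised days or the ratio of rate ratios. Days would match the power assumption; the ratio would match the usual output of the regression. Report within-subgroup effects with confidence intervals, keep alpha/2 for the within-subgroup tests, and state that matching or split verdicts are not evidence about consistency.

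The cost is SAP wording and two model terms per factor, with no new data. There are two downsides. Precision may be poor: at N=400 the half-width is about 13 days on the plan's variance, or roughly 5 to 9 days at correlations of 0.2 to 0.6, so a real difference may be missed. And the answer will depend on the scale chosen, which is why it must be fixed before the results are seen.
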